10.0 Data Safety Monitoring

The proposed study is not a clinical trial; however, all of the procedures will be reviewed and approved by the Indiana University IRB. Any changes in risk levels associated with any of the study approaches will be monitored and will be reported to the IRB. Further, unexpected adverse situations will immediately be reported to the IRB. The PI's will review human subjects protection issues regularly to monitor any adverse situations that have arisen.

11.0 Study Withdrawal/Discontinuation

Participants may choose to withdraw from the study at any time. Deciding not to participate, or deciding to leave the study later, will not result in any penalty or loss of benefits to which the participant is entitled, and will not affect the participants relationship with Indiana University School of Medicine, Riley Hospital for Children, or Indiana University Health. Participants may terminate participation at any time during participation in the study procedures. Participants will be instructed to contact the PI should they wish to withdraw from participation. They will be compensated for the amount of time that they participated in the study (as outlined in reimbursement procedures).

12.0 Statistical Considerations

Statistical plan was developed in consultation with [name], PHD of IUSM Department of Biostatistics for NIH R21 proposal; for this funding mechanism, sample size was estimated at 120 participants; we are requesting IRB approval for a sample size of 300 participants to account for potential future funding for this project.

A sample of 120 children (with estimated distribution: ASD = 60, Non-ASD = 60) will provide the logistic regression models with 83% power for two-sided Wald tests to detect an odds ratio of 1.94, using alpha of 0.05. This calculation assumes that the proportion of ASD at a covariate mean value, versus 1 SD from the covariate mean value, equals 0.34 versus 0.50, for an odds ratio of 1.94. Most of the predictors are continuous variables. Under the worst case scenario for power, in which the predictor is binary and the prevalence of a predictor in one outcome category is 0.50 (e.g., without ASD), 60 in each group will provide 81% power to detect an odds ratio of 3.0 (i.e., when the predictor prevalence in the ASD outcome category is 0.75) using a two-sided Wald test and alpha of 0.05. No more than 5 independent variables will be allowed in the final models, according to the rule of thumb to have at least 10 persons per parameter (i.e., per each 1 *df* independent variable plus intercept) for the smallest sized category of the dependent variable.

Aim #1: Evaluate the diagnostic validity of the EE Hub model of ASD diagnosis in the communitybased primary care setting: Diagnostic validity will be measured by comparing agreement between the EE Hub and expert ASD-specialist on categorical diagnosis (ASD; non-ASD) to estimate diagnostic accuracy indices of sensitivity, specificity, positive predictive value, and negative predictive value. The kappa statistic for chance-corrected agreement, and its 95% confidence interval, will also be calculated.

Aim #2: Determine whether biobehavioral markers can reliably differentiate young children with and without ASD: Differences in metrics between children with and without ASD will be

compared to validate potential biomarkers. Logistic regression with diagnosis as the dependent variable and eye-tracking measures as the independent variables will be used to estimate diagnostic accuracy indices (sensitivity, specificity, positive predictive value, and negative predictive value) at various cut-points on the continuous scale of eye-tracking measures, and to estimate the area under the receiver operator curve (AUROC) with the c-statistic. Bivariate logistic regression will be used to test each eye-tracking measure separately to determine its individual diagnostic efficacy; then multivariable logistic regression will be used, with eye-tracking measures simultaneously entered into the model, to test the joint effect of all eye-tracking measures on their combined diagnostic efficacy with respect to the diagnostic accuracy indices, as well as to determine which eye-tracking measures that do not contribute significantly to diagnostic efficacy will be deleted from the multivariable model.

Aim #3: Determine whether a combination of clinical and biobehavioral measures can be used to accurately predict ASD diagnostic outcome: We will evaluate the predictive efficacy of clinical measures and biobehavioral markers for accurate ASD diagnostic classification, and further determine whether a multivariable combination of clinical and biobehavioral measures may potentially provide a more promising method for ASD diagnostic classification of young children in the primary care setting. Classifier analysis for diagnostic outcome (ASD versus non-ASD as determined by the expert ASD-specialist) will be completed using the multivariable logistic regression procedure described above, except the model will contain clinical measures in addition to eye-tracking measures.

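### Section 12 ties its 83% power to a 60/60 split, but the ASD proportion it assumes (0.34 at the covariate mean, OR 1.94 per SD) implies about 35% ASD

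*Combined protocol and SAP*

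**What the plan says.** All the figures come from the sample-size paragraph of Section 12.0, Statistical Considerations.

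- Sample and split: "A sample of 120 children (with estimated distribution: ASD = 60, Non-ASD = 60".
- Power: this sample "will provide the logistic regression models with 83% power for two-sided Wald tests to detect an odds ratio of 1.94", at alpha 0.05.
- Assumption given for that calculation: "the proportion of ASD at a covariate mean value, versus 1 SD from the covariate mean value, equals 0.34 versus 0.50".
- Type of predictor: "Most of the predictors are continuous variables".
- Fallback case: "Under the worst case scenario for power, in which the predictor is binary" and has prevalence 0.50 in one outcome group and 0.75 in the other, "60 in each group will provide 81% power to detect an odds ratio of 3.0".
- Model size: "No more than 5 independent variables will be allowed in the final models, according to the rule of thumb" of 10 persons per parameter, counting the intercept, "for the smallest sized category of the dependent variable".

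The paragraph names no power formula, no covariate distribution and no R-squared with other predictors. It also says that IRB approval is sought for 300 children in case of later funding, but every power figure is for 120. Sections 6.0 and 7.0 describe consecutive referral, so the ASD/non-ASD split is observed, not fixed by design.

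**The concern.** In a logistic model, the proportion with ASD at the covariate mean and the odds ratio per SD together determine the overall proportion with ASD. If 0.34 of children at the covariate mean have ASD, and the proportion reaches 0.50 only 1 SD away, a sample that is half ASD is not expected. The 83% and the 60/60 split therefore appear to belong to different designs.

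This matters because the 81% for a binary predictor and the number 5 in the predictor cap both need 60 children in the smaller group. If about 35% ASD is the real expectation, the plan's own worst case drops below 80%, and its own rule allows fewer predictors than it prints. The cap bears directly on Aims 2 and 3: Section 2.0 lists five eye-tracking measures (pupil dilation, pupillary light reflex, blink rate, looking time, saccadic latency), and Aim 3 adds clinical measures to the same kind of model.

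**Working it through.** **Inputs (Section 12.0).** N = 120; split 60/60; two-sided alpha 0.05; ASD proportion 0.34 at the covariate mean and 0.50 at 1 SD; OR 1.94; binary case 0.50 versus 0.75 with 60 per group; 10 persons per parameter. Added assumption: standard normal covariate, relaxed in step 3.

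**1. Odds ratio.** (0.50/0.50) / (0.34/0.66) = 1.941, so b = ln 1.941 = 0.6633 per SD. This agrees with the printed 1.94.

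**2. The 83%.** The Whittemore/Hsieh 1989 formula for one normal covariate is

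N = (1.96 + z_power · exp(−b²/4))² · (1 + 2Pδ) / (P·b²), with δ = [1 + (1 + b²)·exp(5b²/4)] / [1 + exp(−b²/4)].

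Here b² = 0.440, exp(−b²/4) = 0.896 and δ = 1.844. Solving for z_power at N = 120:

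- P = 0.34: √(120 × 0.1496 / 2.254) = 2.822; z = (2.822 − 1.960) / 0.896 = 0.962; power 83.2%.
- P = 0.50: √(120 × 0.2200 / 2.844) = 3.047; z = (3.047 − 1.960) / 0.896 = 1.213; power 88.7%.

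So the printed 83% is reproduced with 0.34 at the mean and not with 0.50. This is suggestive, not decisive. At P = 0.50 an unstated R-squared of 0.136 to 0.157 gives 83.5% to 82.5%, which also rounds to 83%. Other methods give, at 0.34 and 0.50 respectively:

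| Method, no R-squared | 0.34 | 0.50 |
|---|---|---|
| Fisher-information Wald | 86.0% | 88.4% |
| Simulated Wald test | about 90% | 92–93% |
| Hsieh 1998 | 93.1% | 95.3% |

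The 1998 formula needs an R-squared of 0.28 (at 0.34) or 0.36 (at 0.50) to come down to 83%.

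**3. Implied overall ASD proportion.** Average expit(logit(0.34) + bZ) over Z ~ N(0,1): 0.3534. Then 0.3534 × 120 = 42.4, so about 42 ASD and 78 non-ASD. The sign of b makes no difference for a symmetric covariate. Other covariates with mean 0 and SD 1:

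- uniform 35.4%; t with 5 df 35.2%;
- exponential, right-skewed 34.6%, left-skewed 35.7%;
- all two-point distributions 33.2% to 35.9%.

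None comes near 50%. A 50% overall share follows if the proportion at the mean is 0.50; it is then 0.66 at +1 SD and 0.34 at −1 SD.

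**4. Binary predictor, 0.75 versus 0.50.** In the pooled formula, power = Φ[(0.25 − 1.96·s₀)/s₁], where s₀ and s₁ are the standard errors under the null (pooled) and the alternative.

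- 60/60: pooled proportion 0.625, s₀ = 0.0884, s₁ = 0.0854, z = 0.899, power 81.6%. This matches the printed 81%.
- 42/78: pooled proportion 0.5875, s₀ = 0.0942, s₁ = 0.0876, z = 0.746, power 77.2%.

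| Method | 60/60 | 42/78 | Loss (points) | 106/194 (N = 300) |
|---|---|---|---|---|
| Pooled | 81.6% | 77.2% | 4.4 | 99.2% |
| Exact enumeration of Wald test | 81.4% | 78.1% | 3.3 | 99.2% |
| Wald log-OR approximation | 79.5% | 74.0% | 5.5 | 98.5% |

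The N = 300 column uses 0.3534 × 300 = 106.

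**5. Predictor cap.** Parameters allowed = floor(smaller group / 10), less 1 for the intercept.

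- 60: 6 − 1 = 5, the printed number. 50 to 59: 4. 42: 4 − 1 = 3.
- At N = 120 the smaller group reaches 60 only with an exact 60/60 split. With a true ASD rate of 50% and binomial sampling, the rule gives 5 in 7.3% of samples, 4 in about 87% and 3 or fewer in 5.5%.
- With a true rate of 35.3% it gives 4 or 5 in 8.9%, 3 in 62.0% and 2 or fewer in 29.2%.
- To expect 60 ASD cases at 35.3% takes 60 / 0.3534 ≈ 170 children. At N = 300 the cap of 5 holds under either rate.

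**The case against.** The case on the other side has four parts.

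- **The headline power is not overstated.** This stands. If 60/60 is right, 83% is conservative by the unadjusted methods; if 0.34 is right, 83% is reproduced or exceeded. The total sample size and the test are not in question.
- **It may be a slip of wording.** The text gives no direction for the 1 SD. With 0.50 at the mean and 0.34 at 1 SD below, OR 1.94 and 60/60 both hold, and so do the 81% and the 5. This is possible and cannot be excluded. But it reverses the printed order, and the 1989 formula then gives 88.7%, so 83% would need an unstated R-squared. The sentence needs correcting on this reading too.
- **The cap already refers to the smaller outcome group and is only a ceiling.** Read strictly, the rule yields 3 at 42/78 without any edit. That is fair, but the text prints a constant and does not say it is recomputed from the observed groups, and at N = 120 the constant meets the rule only at exactly 60/60. The sampling variation behind this is a separate matter from the 0.34/0.50 conflict and would remain after that was corrected.
- **The consequences are limited.** Most predictors are continuous, the 5.5-point loss comes from an approximation that does not itself reproduce 81%, and everything disappears at N = 300. All true. The fairer range for the binary loss is 3.3 to 4.4 points. The 300 depends on possible future funding, however, and the power statement is for 120.

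**Conclusion.** The concern holds. As printed, the 60/60 split and the 0.34 at the covariate mean cannot both describe the design behind the 83%. That mismatch is firm: it needs only a logistic model and a covariate scaled to SD 1, and no covariate shape tried gave more than 35.9% ASD. Which figure is the intended one cannot be settled from the document.

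The consequences are conditional on 0.34 being the intended figure and on N = 120: an expected split of about 42/78, binary-predictor power of about 77% to 78% by the methods that reproduce the printed 81%, and 3 predictors instead of 5 under the plan's own rule. If 60/60 is intended, the 81% and the 5 stand as planning values and only the assumption and its power need restating. Continuous-predictor power is adequate either way. This should be corrected before analysis, but it does not undermine the study.

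**What to change.** Use one ASD prevalence throughout Section 12.0, and name the power formula and any R-squared.

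- **If 60/60 is intended:** state 0.50 at the mean versus 0.66 at +1 SD (or 0.34 at −1 SD), with power of about 89% by the 1989 formula (92–93% by simulation), or give the R-squared that brings it to 83%. Keep the 81% and the 5 as planning values.
- **If 0.34 is intended:** state the split as about 42/78, the binary-predictor power as about 77% (pooled; 78% exact Wald, 74% Wald log-OR), and the planning cap as 3 at N = 120.
- **In either case:** define the final-model cap as the smaller of 5 and floor(smaller observed group / 10) − 1, because consecutive referral does not control the split.

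The cost is about four sentences, with no extra children and no change of test or endpoint. The price is fewer predictors in the final models whenever the smaller observed group is under 60. Keeping 5 as a ceiling means the plan is not loosened if enrolment goes beyond 120.

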opportunities for early, evidence-based interventions at the time of optimal neuroplasticity. The current proposal addresses this need by linking a community-based clinical evaluation model with the utilization of biobehavioral markers to test the diagnostic efficacy of these approaches for accurately classifying young children with ASD in a high-risk community-referral sample in the primary care setting.

Scientific Premise for Aim #1

Pediatric advocacy groups [16] have highlighted the challenges around access to early diagnostic services for children at risk for ASD and have called for the evaluation of new models of care delivery [5]. To date, three small studies have investigated whether training community-based clinicians to provide ASD diagnostic services is a feasible endeavor. McClure and colleagues [7] trained local teams of health professionals to perform ASD assessment. Of 33 children evaluated, there was 87% diagnostic agreement with the expert ASD evaluation team and a significant reduction in wait time for evaluations. Warren and colleagues [9] reported on a program in which pediatricians were trained to diagnose young children with ASD in community practice settings. In this pilot study of 21 children ages 22-37 months, there was 71% agreement between pediatrician diagnosis and independent expert ASD evaluation. In follow-up to this work, Swanson and colleagues [8] used the same training model to measure the accuracy of ASD diagnostic evaluation in a sample of 14 children with 86-93% diagnostic agreement between local pediatric providers and independent expert evaluation. Limitations to these important preliminary studies include small sample sizes and limited variability in child diagnosis (including under representation of those ultimately diagnosed with ASD and those with co-occurring intellectual disability) and baseline level of knowledge in community providers. Yet, these studies represent promising preliminary evidence for implementation of innovative models in which local pediatric health professionals provide ASD diagnostic evaluations in community settings. The proposed project builds on this preliminary evidence by testing an existing statewide model of early ASD diagnosis in the primary care setting with a high-risk community-referral sample of children. We will determine the diagnostic validity of this existing model by comparing diagnostic agreement between primary care providers and independent expert ASD evaluation.

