7.0 Study Procedures

Children (ages 14-48 months) are referred to the EE hub by their primary care provider when there is concern about a neurodevelopmental disability (e.g., parent/PCP concern or failed developmental screener; i.e., MCHAT-R/F). Children are evaluated by a pediatric health professional at the EE Hub with a standard battery of developmental history, physical exam, and behavioral measures; a diagnosis is made when appropriate and the parent/caregiver(s) receive the diagnosis and next step recommendations. For the purpose of this study, the pediatric health professional will complete a diagnostic certainty form indicating whether or not they provided a diagnosis of autism spectrum disorder and how certain they are about the diagnostic outcome [1-5 Likert scale; 1=completely certain; 5=not at all certain].

The EE Hubs will refer a consecutive sample of children for follow-up evaluation by study personnel (diagnostic evaluation overseen by PI/ASD Specialist: [name]). The EE Hub pediatric health professional will provide the parent/caregiver(s) with information about the study via a study brochure. If the parent/caregiver(s) is interested in participating, the parent will complete and sign the contact information sheet and it will be sent to the study team. The research coordinator will contact the parent/caregiver(s) by phone to provide additional information about the study. If the parent/caregiver(s) agrees to participate, the research coordinator will schedule a follow-up evaluation, at no cost to the child's family, at the local EE Hub site. This follow-up visit will occur within 16 weeks of the original EE Hub evaluation. During this call, the parent/caregiver(s) will provide verbal consent to have a battery of caregiver-report questionnaires sent to them by mail or via secure electronic link (i.e., Redcap) to return prior to or at the time of the research visit. This process will reduce face-to-face time required for the research visit.

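### Is the 81% power for a binary predictor mislabelled as a worst case in Section 12?

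*Combined protocol and SAP*

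**What the plan says.** Section 12.0 (Statistical Considerations) plans on "A sample of 120 children (with estimated distribution: ASD = 60, Non-ASD = 60"). It first gives power for a continuous covariate (83% for an odds ratio of 1.94 per SD) and adds: "Most of the predictors are continuous variables". The fallback for a binary predictor comes next: "Under the worst case scenario for power, in which the predictor is binary and the prevalence of a predictor in one outcome category is 0.50". Non-ASD is named as an example of that category. The result is that "60 in each group will provide 81% power to detect an odds ratio of 3.0", which is the case "when the predictor prevalence in the ASD outcome category is 0.75", with a two-sided Wald test at alpha 0.05.

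No other prevalence is given. Under Aim #2 in the same section, accuracy is to be estimated "at various cut-points on the continuous scale of eye-tracking measures". Aim #3 adds clinical measures to the model without listing them.

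**The concern.** Read literally, the sentence makes two conditions part of the worst case: the predictor is binary, and its prevalence in one group is 0.50. A reader could then take 81% as a floor for any binary predictor with an odds ratio of 3.0.

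A prevalence of 0.50 maximises the variance of a single proportion, which makes it the cautious choice when a difference in proportions is the target. For an odds ratio the direction reverses: sparse cells inflate the variance of the log odds ratio, so prevalences far from the middle cost power. If an important predictor were rare or very common, the design would have less power than the label suggests, and this is the only statement about binary predictors in the sample-size justification.

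**Working it through.** **Inputs, all from Section 12.0:** n = 60 per group; prevalence p0 = 0.50 without ASD and p1 = 0.75 with ASD; two-sided Wald test, alpha 0.05 (z = 1.96). Every other prevalence below is an illustrative assumption.

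**1. Reproduce the plan's figure.**
- Odds ratio = (0.75/0.25)/(0.50/0.50) = 3.0.
- Large-sample Wald: SE = √[1/(60·0.50·0.50) + 1/(60·0.75·0.25)] = √(0.0667 + 0.0889) = 0.394. Then ln 3/SE = 1.0986/0.394 = 2.785, and Φ(2.785 − 1.960) = 79.5%.
- Pooled two-proportion formula: 81.6%.
- Exact power of the log-odds-ratio Wald test, summing binomial probabilities over all 61 × 61 tables and counting zero-cell tables as non-significant: 81.4%.

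The stated 81% is confirmed.

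**2. Hold the odds ratio at 3.0 and move p0**, with p1 = 3p0/(1 − p0 + 3p0):

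| p0 (non-ASD) | p1 (ASD) | Exact Wald power |
|---|---|---|
| 0.10 | 0.250 | 57.4% |
| 0.20 | 0.429 | 77.6% |
| 0.25 | 0.500 | 81.4% |
| 0.37 | 0.638 | 85.5% (about the maximum) |
| 0.50 | 0.750 | 81.4% (the plan's case) |
| 0.60 | 0.818 | 75.7% |
| 0.70 | 0.875 | 65.1% |

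The equality at 0.25 and 0.50 is exact by symmetry, because swapping presence with absence and one group with the other turns 0.50/0.75 into 0.25/0.50. The large-sample Wald, pooled and unpooled formulas give the same band. For a predictor less common in ASD (odds ratio 1/3) the band mirrors to non-ASD prevalences of 0.50 to 0.75. So 0.50 is an edge of the favourable band and not a minimum.

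**3. Hold the difference at 0.25 instead**, p1 = p0 + 0.25:

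| p0 | p1 | Exact Wald power |
|---|---|---|
| 0.10 | 0.35 | 92.0% |
| 0.25 | 0.50 | 81.4% |
| 0.375 | 0.625 | 80.3% (minimum) |
| 0.50 | 0.75 | 81.4% (the plan's case) |
| 0.65 | 0.90 | 92.0% |

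The plan's case is 81.4 − 80.3 = 1.1 points above the minimum. By the pooled formula the minimum is 78.9%, and the gap is 81.6 − 78.9 = 2.7 points. On this reading the label is close to correct.

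**4. Size on the effect scale.** The odds ratio needed for the same 81.4% power is 2.82 at p0 = 0.37, 3.00 at 0.25 and 0.50, 3.15 at 0.20, 3.30 at 0.60 and 4.06 at 0.70. From 0.20 to 0.60 the detectable effect therefore stays between 2.82 and 3.30.

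**5. Is there a binary predictor to which this applies?** None is named for any model. The clearest two-level measure is the Hub clinician's form (Section 7.0), "indicating whether or not they provided a diagnosis of autism spectrum disorder", and the plan does not say that it enters a regression. If it did, take the lowest agreement cited in Section 1.0 ("there was 71% agreement between pediatrician diagnosis and independent expert ASD evaluation") and assume that it holds equally in both groups. Prevalences would then be 0.29 and 0.71, the odds ratio (0.71/0.29)² = 5.99, and exact power 99.8%. That rests on a 21-child pilot and is only a rough guide.

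**The case for a change.** The strongest case for acting is that the statement is false as written for the effect measure it names. The prevalence is joined to the worst case by its grammar, the effect is stated as an odds ratio, and at a fixed odds ratio of 3.0 power can be well below 81%. Aim #3 leaves its clinical measures unlisted, and a remark that most predictors are continuous implies that some may not be. Correcting it would take a few words.

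The arithmetic in that case stands. Its weight does not. The label comes directly after the remark on continuous predictors, so its main job is to say that the binary case is the less favourable kind, which is not in dispute. The plan also spells its effect out as a pair of prevalences, and for a fixed gap between them the label is about right. The larger shortfalls need prevalences found nowhere in the documents: 65.1% requires a feature present in 70% of children without ASD and 87.5% of those with it. Writing such assumed values into the protocol would add figures with no source.

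**Conclusion.** No change is called for. The 81% is correct for its stated inputs, and only a two-word description goes too far. Taken as a floor at a fixed odds ratio of 3.0 it fails outside non-ASD prevalences of 0.25 to 0.50 (0.50 to 0.75 if the predictor is less common in ASD). Taken as a contrast with continuous predictors it does its job, and for a fixed 0.25 difference it is right to within 1.1 points by exact Wald power.

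Rewording would not alter the sample size, any model, or anything the study can conclude, and no planned analysis is shown to lose power. This rests on the 60/60 split in Section 12.0 and on no binary predictor being named. An analyst who later adds one will judge its precision from the confidence interval for its odds ratio, whatever the planning sentence called the scenario.

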4.0 Eligibility Criteria

Inclusion Criteria

• The target sample of participants will be children, ages 14-48 months referred to the EE Hubs due to a screen-positive result on the MCHAT-R/F and/or parent/caregiver or pediatric provider concerns about development.

Exclusion Criteria

• Children must have a parent/caregiver(s) who speaks English to them such that 1) they are exposed to spoken language in English or 2) the child speaks and/or understands English. Given age and disability of children in the study, some children may not yet have developed functional receptive or expressive language. However, children who do not meet the above criteria will not be included in this research due to the significant language demands of study procedures and some assessments not being validated in languages other than English.

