6.0 Enrollment/Randomization

Subjects will be identified by the EE Hubs. Parent/caregiver(s) of a consecutive sample of children (ages 14-48 months) will be given a study information brochure and asked if they are interested in learning more about the study. If interested, parent/caregiver(s) will fill out a contact information sheet, which will be sent to the research coordinator. The research coordinator will contact the parent/caregiver(s) by phone/email to provide additional information about the study. If the parent/caregiver(s) agree to participate, the research coordinator will schedule the research visit. Written informed consent and authorization (to share evaluation results between EE Hub, child's primary care, and research team will be obtained at the time of the appointment.

Blinded Evaluation Process: Because the family will have received an initial diagnosis for their child during the evaluation at the EE Hub, there is risk for the family to share this information with the blinded ASD specialist, thereby introducing bias into the final diagnostic decision. In order to mitigate this bias, families will be informed on several occasions (i.e., at the time of referral, during the consenting process, and by the blinded ASD-specialist) that they are not to share their child's EE Hub diagnosis with the ASD specialist.

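### Aim 2 tests eye-tracking markers without an age term in unmatched referrals aged 14-48 months, so it cannot show whether a marker differs by ASD at a given age; a prespecified age-adjusted test would be a cheap addition

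*Combined protocol and SAP*

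**What the plan says.** Section 12.0 (Aim #2) specifies "Logistic regression with diagnosis as the dependent variable and eye-tracking measures as the independent variables". It works in two stages. First, "Bivariate logistic regression will be used to test each eye-tracking measure separately to determine its individual diagnostic efficacy". Then all measures enter one model, which gives their joint accuracy and is used to "determine which eye-tracking measures that do not contribute significantly to diagnostic efficacy will be deleted from the multivariable model". The same section says that marker differences between children with and without ASD will be compared in order to establish candidate biomarkers.

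On the sample, Section 4.0 states "The target sample of participants will be children, ages 14-48 months", and Section 6.0 states "Parent/caregiver(s) of a consecutive sample of children (ages 14-48 months) will be given a study information brochure". The diagnostic groups form afterwards, from the specialist's diagnosis. On timing, Section 7.0 states "This follow-up visit will occur within 16 weeks of the original EE Hub evaluation".

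On size, Section 12.0 plans 120 children (60 ASD, 60 non-ASD), with "83% power for two-sided Wald tests to detect an odds ratio of 1.94", and adds "No more than 5 independent variables will be allowed in the final models".

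The text reviewed does not match on age, stratify by it or adjust for it, and it plans no table of age by diagnosis. The Section 5.0 diagram and the IRB documents to which Section 17.0 refers were not available.

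**The concern.** Children of 14 and 48 months may differ in pupil size, blink rate or saccadic latency for reasons of maturation. Section 3.0 describes age-referenced scoring for the ADOS-2 comparison score and standardised scores for the MSEL and VABS-3. It states no such reference for the eye-tracking measures. Because the groups come from consecutive referrals, nothing makes their ages equal.

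If a marker tracks age and the groups differ in age, an unadjusted p-value mixes the two. A marker with no ASD effect at a given age could then be reported as an ASD biomarker. With the gap in the other direction, a real one could be dropped. No planned output would let a reader tell these cases apart.

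**Working it through.** **1. The plan's power figure.** Inputs from Section 12.0: ASD proportion 0.34 at the covariate mean and 0.50 at 1 SD, n=120, two-sided alpha 0.05. The odds ratio is (0.50/0.50)/(0.34/0.66) = 1.941, so b = ln(1.941) = 0.663 and b² = 0.440. Hsieh's (1989) logistic formula is

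n = [z(α/2) + exp(−b²/4)·z(β)]² (1 + 2Pδ)/(P·b²), where δ = [1 + (1+b²)exp(5b²/4)]/[1 + exp(−b²/4)].

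With P=0.34, δ = 1.844, 1+2Pδ = 2.254 and exp(−b²/4) = 0.896. At n=120, √(120×0.34×0.440/2.254) = 2.822, z(β) = (2.822−1.960)/0.896 = 0.962, and power is 83.2%. The stated 83% reproduces. It has no allowance for a covariate, so it covers an unadjusted predictor.

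**2. Inputs the documents do not give.** These are the marker-age correlation r and the age gap D in SD units; both are assumptions here. If ages are uniform over 14-48 months, the SD is 34/√12 = 9.8 months, so 0.3 SD is 2.9 months and 0.5 SD is 4.9 months.

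**3. Marker with no ASD effect given age, 60 per group.** Take marker = r·age + √(1−r²)·noise, with ASD ages shifted by D. The groups then differ by rD. The unadjusted rejection rate is about Φ(λ−1.96) + Φ(−λ−1.96) with λ = rD√30, and the marker's AUROC is about Φ(rD/√2). Simulated values are Wald tests in logistic models, 8,000 replicates.

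| r | D | rD | Formula | Simulated, no age term | AUROC |
|---|---|---|---|---|---|
| 0.2 | 0.3 | 0.06 | 6.2% | 6.4% | 0.517 |
| 0.3 | 0.3 | 0.09 | 7.8% | 8.0% | 0.525 |
| 0.5 | 0.3 | 0.15 | 13.0% | 12.2% | 0.542 |
| 0.2 | 0.5 | 0.10 | 8.5% | 8.0% | 0.528 |
| 0.3 | 0.5 | 0.15 | 13.0% | 12.5% | 0.542 |
| 0.5 | 0.5 | 0.25 | 27.8% | 26.7% | 0.570 |

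With r=0 or D=0 the unadjusted rate is 4.6-4.9%. With age in the model it is 4.6-5.4% in every cell. For uniform ages, age alone has AUROC 1 − (1−D/√12)²/2, which is 0.58 at D=0.3 and 0.63 at D=0.5.

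**4. Masking.** For a real 0.5 SD marker and an opposite 0.5 SD age gap, single-marker power at r=0.2, 0.3 and 0.5 is 58%, 47% and 26% without age, against 76%, 78% and 85% with age.

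**5. Joint model of five markers.** With D=0.5, one age-related null marker survives deletion in 9%, 13% and 27% of trials without age (r=0.2, 0.3, 0.5) and in about 5% with age.

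**6. How far this depends on linearity and equal spread.** Suppose the marker plateaus with age and ASD ages span only 60% of the range (3,000 replicates, linear-model test of the group term). A test with one linear age term then rejects 8-10% at a marker-age weight of 0.3 and 13-23% at 0.5. In the same setting with equal mean ages, the unadjusted test rejects 11% and 22%. So equal mean ages do not guarantee 5%, and neither does a single linear age term.

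**7. Power if the odds ratio of 1.94 is read as age-adjusted.** Replace n by n(1−R²). For R² = 0.04, 0.09 and 0.25 the effective n is 115.2, 109.2 and 90.0, z(β) is 0.899, 0.817 and 0.540, and power is about 82%, 79% and 71%. Keeping 83% would take about 125, 132 or 160 children.

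**The case against.** The strongest reply is that Aim 2 asks a marginal question: does the marker separate referred children with ASD from those without? For that question the unadjusted test is correct. In the cells of step 3 the marker really does discriminate slightly (AUROC up to 0.57), so rejecting is no error. This stands. A reader might infer that the planned tests are invalid or have inflated type I error, and the documents do not support that. The excess over 5% is an error only against the null of no difference at a given age, which becomes relevant when a marker is put forward as a biomarker of ASD.

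The size of the harm is also unsupported by the documents. Their one remark on age-related change (Section 1.0, premise for Aim 2) concerns the first year of life, below the study range. At small r and gap the rate barely moves. Ordinary multiplicity matters more in many settings: with five null markers, at least one is kept in 22-23% of trials even with age in the model.

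Two stronger remedies are tempting: forcing age into the deletion step, and resting every ASD claim on the age-adjusted test. Neither follows. Deletion serves the classification question, and an age-only adjustment leaves developmental level untouched, although the protocol wants to separate ASD from other neurodevelopmental disabilities. A reader might also point to 300 children, where the unadjusted rate would be higher still. Section 12.0 gives 300 only as an IRB request against possible future funding.

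**Conclusion.** The point holds as a cheap improvement. Aim 2 has no age term, the design does not balance age, and no planned analysis separates an ASD difference from an age difference. The planned unadjusted tests, sensitivity, specificity, predictive values and AUROC remain valid for a marker used without age in this referral sample.

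The consequence depends on two unknowns. Given a linear relation and equal spread, it ranges from negligible (r or gap near zero) to about one false age-conditional claim in four at r=0.5 with a 0.5 SD gap. A reader might infer from this that the markers are confounded by age, or that the stated power is wrong. The documents show neither: they contain no data on marker-age correlation or on age by group, and 83% is correct for an unadjusted predictor.

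**What to change.** Keep all planned unadjusted analyses and the planned deletion step, and add to Section 12.0:

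1. A prespecified age-adjusted logistic test of each marker, using age in months at the research visit, with a check for a nonlinear age relation. Visit age is the right one because the visit can fall up to 16 weeks (3.7 months) after the Hub evaluation.
2. As a sensitivity analysis, the joint model with age added.
3. A table of age by diagnosis and the AUROC of age alone.
4. A statement that no marker will be described as differing by ASD independently of age unless the age-adjusted result supports it.
5. A note that the 83% power refers to an unadjusted predictor.

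No new data are needed, since age is known from eligibility. The cost is one degree of freedom per added model, and slightly more if a nonlinear term is used. If age differs by 0.5 SD between groups but is unrelated to the marker, power for a 0.5 SD marker falls from about 77% to 74%. If the Section 12.0 diagram or IRB documents already cover age, one cross-reference is enough.

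Section 2.0 names five measures and Section 3.0 three. With five, the sensitivity model has seven parameters including the intercept, which would need 7×10 = 70 children in the smaller group against 60 planned. The five-variable cap applies to final models, so this does not breach it, but the result should be labelled as a sensitivity analysis.
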